Model parameter estimates will be generated by fitting three MCMC chains. Each chain will involve at least 10,000 burn-in samples and at least 200,000 additional samples, which will be thinned by at least 5. More samples and more thinning will be done if necessary, to produce good sampling of the posterior. The final MCMC chains will have at least 120,000 useable samples to estimate the posterior distributions necessary for making inference about the treatment effects, (relative risk or outcome difference).

For binary outcomes, the outcome for the j^{th} infant from the i^{th} center will have the following form:

$$y_{ij} = \begin{cases} 0 & \text{survival without moderate / severe disability at 18-22 months corrected age} \\ 1 & \text{death or moderate / severe disability at 18-22 months corrected age} \end{cases}$$

The main covariates will have the form:

$$trt_{ij} = \begin{cases} 0 & \text{normothermia} \\ 1 & \text{whole body hypothermia} \end{cases}$$

$$enceph_{ij} = \begin{cases} 0 & \text{mild encephalopathy} \\ 1 & \text{moderate or severe encephalopathy} \end{cases}$$

The logistic model used for analysis of binary outcomes on the relative risk and risk difference scale will have the following form:

$$y_{ij} \sim \text{Bernoulli}[\pi_{ij}], \text{ where}$$

$$\text{logit}[\pi_{ij}] = \alpha_i + \theta_1 \cdot \text{enceph}_{ij} + \theta_2 \cdot \text{trt}_{ij}$$

β_1, β_2 will have priors as specified in Section 6.5.3

α_i will be the random intercepts due to center. Prior specified in Section 6.5.3.

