6.5.2 Covariates

All regression models will adjust for:

- level of encephalopathy at randomization and
- center (as a random effect).

The planned number of enrolling centers is 18, and center will be included in the linear component of the model as an additive random effect.

In addition to adjusting for level of encephalopathy and center as a random effect, sensitivity analyses will be completed by selecting baseline covariates that differ across the two treatments. These covariates will be selected from those covariates listed in section 5.3.

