6.5.5 Final Analysis

The final analysis will occur after 168 infants have completed the trial, as specified earlier. The final analysis will not occur until all enrolled infants have a primary outcome determination, i.e. have the primary endpoint value assigned, classified as withdrawn without primary outcome assigned, or deemed lost to follow-up. Part of determining primary outcome of enrolled infants will involve masked adjudication of outcomes for infants who have an indeterminable outcome based on partially collected follow-up information. Once all enrolled infants have reached final status and primary endpoints determined, the clinical database will be exported, and study analysis datasets created. At that point, the analysis datasets will be considered “locked” and any further adjustments to the clinical datasets will not be included in the analysis datasets.

The final analysis will involve posterior distribution estimation for the effect of hypothermia relative to normal cooling. For binary outcomes, the effect will be the adjusted relative risk and adjusted risk differences calculated from a binomial regression model with logit link and post processing of

predicted outcome probabilities. For count outcomes, the effect will be the adjusted relative risk from the two groups obtained using negative binomial regression. For ordinal outcomes, the effect will be the adjusted odds ratio calculated from the cumulative logits.

For treatment relative risk estimation, posterior probabilities of >0%, >5%, >10% and >20% decrease in binary outcomes will be calculated. If θ is the relative risk defined as risk in cooling group over risk in control group, then the above specified posterior probabilities are, $\Pr(\theta < 1 | X)$, $\Pr(\theta < 0.95 | X)$, $\Pr(\theta < 0.9 | X)$, $\Pr(\theta < 0.8 | X)$. In addition to posterior probability calculations, graphical displays of the posterior distribution and appropriate 95% credible intervals for the over-all relative risk will be created. Finally, forest plots of the center level relative risks and 95% credible intervals will be created.

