- Posterior plot of treatment effect
- Posterior median and posterior standard deviation
- 95% credible interval
- For relative risk, posterior probabilities of >0%, >5%, >10%, and >20% decrease in the primary outcome will be calculated
- For risk difference, posterior probabilities of >0%, >1%, >2%, >3%, and >5% decrease in primary outcome will be calculated
- forest plot of the center level effect and 95% credible intervals.

If the FAS analysis of the primary outcome results in any clinically notable findings, then the primary outcome may also be analyzed in an exploratory fashion using the PP population.

Analysis of Secondary Outcomes

With respect to secondary outcomes, analyses will follow the same process as the primary outcome analysis defined above. See MockTablesAppendix.docx for list of selected variables.

Analysis of Safety (AE) and Hospital Outcomes

Safety and hospital outcomes listed in Sections 6.2 and 6.3 will be analyzed using the FAS population and if necessary, the PP population using relative risk models, proportional odds models, or Negative Binomial models, depending on the type of outcome.

With respect to binary safety outcomes, the estimated posterior distribution of relative risk, θ , based on the data and the neutral prior will be used to determine posterior probabilities of harm from the intervention, $\Pr(\theta > 1 | X)$, as well as 95% credible intervals.

For ordinal safety outcomes, the estimated posterior distribution odds ratio for the cumulative logits, ϕ , will be estimated based on the data and the neutral prior. In addition, posterior probabilities of harm, $\Pr(\phi > 1 | X)$, and 95% credible intervals of ϕ will be calculated.

For count type safety outcome, the estimated posterior distribution of the treatment mean rate, ϕ , will be estimated based on the data and the neutral prior. In addition, posterior probabilities of harm, $\Pr(\phi > 1 | X)$, and 95% credible intervals of ϕ will be calculated.

Analysis of Ultrasound, CT scan, MRI and encephalopathy outcomes

Ultrasound, CT scan, MRI, and encephalopathy outcomes will be analyzed using the FAS population. Head ultrasounds, CT scans, and brain MRIs will be summarized by treatment and time (prior to intervention, during intervention, after intervention, any time). Summaries will be created for number of babies with any abnormal findings during time period data recorded, and for total events across all babies during any time period.

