6.5.8 Subgroup Analysis

The primary outcome will be reanalyzed for subgroup exploratory analyses. These analyses will be completed using the FAS population. These subgroup analyses will utilize interactions within the risk difference model defined in section 6.5.1 to study treatment heterogeneity and to estimate effects within subgroups when the treatment heterogeneity is clinically important. In each case, the subgroup variable will be added to the model, if not already in the model, along with the interaction between the subgroup variable and the treatment variable. These subgroup analyses will use modified versions of the models that included potentially important covariates and described in sections 6.5.1 and 6.5.2. Only the neutral priors will be considered in these analyses, and the priors for the interaction terms will be the same priors applied to the treatment groups as described in sections 6.5.3 and 6.5.4. In these models with interaction terms, effect coding will be used for treatment and level of encephalopathy instead of reference cell coding.

Reporting of subgroup analyses will include summary statistics from the Posterior distribution of the treatment effect within each level of the subgroup as well as generation of forest plots and posterior plots when deemed useful by the Preemie Hypothermia subcommittee. In addition to estimation of Posterior treatment effects within each level of the subgroup, summary posterior statistics of differences /ratios of treatment effects from all possible combinations of subgroup level pairs will be estimated (possible calculations here will be: differences in differences or ratio of ratios, since they will represent or be functions of effects that make up the interaction term(s) and other combinations not used to create interaction terms in the model given model parameterization). Summary posterior statistics will include medians, 95% credible intervals, and posterior probabilities of benefit.

The subgroups that will be considered are:

- Sex
- Center, if model estimation will allow it
- Race, provided we have sufficient diversity in the study population. At least two levels making up at least 20% each, and at least three levels represented.
- GA (3 levels: 33, 34, and 35 weeks)
- Infants who qualified on seizures alone vs. not (2 levels)
- Infants who had a baseline temperature < 36.5 °C vs. not (2 levels)
- Infants who had a baseline temperature < 35.0 °C vs. not (2 levels)

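### The center-level forest plots required in SAP 6.5.5 come from a model with one common odds ratio, so every center shows the same direction and the same probability of benefit by construction

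*SAP*

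**What the plan says.** SAP 6.5.1 gives the binary-outcome model as `logit(p_ij) = alpha_i + theta1*enceph_ij + theta2*trt_ij`. The alpha terms "will be the random intercepts due to center", and theta2 carries no center index. SAP 6.5.2 confirms the structure: "The planned number of enrolling centers is 18, and center will be included in the linear component of the model as an additive random effect". SAP 6.5.3 gives one SD hyperprior for the center effect, a half-normal with SD 1, and none for a center-varying treatment effect. RR and RD are obtained by predicting each infant's risk under both treatments from this one fit.

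SAP 6.5.5 then asks for center-level displays: "forest plots of the center level relative risks and 95% credible intervals will be created", with a parallel sentence for risk differences. Its list of outputs for each of the six primary analyses (RR and RD, each under three priors) includes a "forest plot of the center level effect and 95% credible intervals".

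SAP 6.5.8 lists, among exploratory subgroups analyzed with a treatment interaction, "Center, if model estimation will allow it". It uses the neutral prior only, and forest plots there are made when the subcommittee finds them useful. It does not mention the 6.5.5 plots.

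**The concern.** A forest plot by center is ordinarily read as a check on whether the effect holds across sites. The trial is unmasked (SAP 3.1), with about 9 infants per planned center, so readers have little else by which to judge site dependence. If the model behind the plot allows only one odds ratio, agreement in direction is an assumption displayed as though it were a result. The spread that does appear reflects differing baseline risk, yet a reader could take it for differing efficacy. A center whose own infants fared worse under cooling would still be plotted on the side of benefit whenever the overall estimate is.

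**Working it through.** **Inputs from the SAP.** Model form and post-processing (6.5.1); additive center effect and 18 planned centers (6.5.2); treatment prior Normal(0, 0.7072) on the log odds ratio and half-normal(0,1) for the center SD (6.5.3); 168 infants (6.5.5). Assumed, because the SAP does not give them: center control risks, center sizes, and true center effects in the simulations. RD is hypothermia minus normothermia, as in 6.5.1.

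**1. The stated priors reproduce.** Neutral: exp(0 ± 1.96 × 0.7072) = exp(±1.386) = 0.25 to 4.00, as stated. Skeptical and enthusiastic give 0.275–4.399 and 0.188–2.999, against 0.28–4.40 and 0.19–3.00. No figure in the SAP is disputed.

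**2. The identity.** Take any posterior draw and any infant in center i, and let b = alpha_i + theta1 × enceph. The risk is expit(b + theta2) under hypothermia and expit(b) under normothermia. Since expit is increasing, the first is smaller if and only if theta2 < 0. This holds for every infant in every center at once, so it also holds for a center average, a ratio of averages, or pooled infant-level draws. Hence, for every center i,

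Pr(RR_i < 1) = Pr(RD_i < 0) = Pr(theta2 < 0).

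Two consequences follow. All center posterior medians lie on the same side of no effect. Equal-tailed 95% intervals either exclude no effect in every center or in none. RR and RD under a given prior come from the same fit, so the six plots carry only three distinct probabilities of benefit, one per prior.

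**3. What can still vary.** With common odds ratio OR and control risk p, RR = OR / (1 − p + OR × p) and RD = p × RR − p. For OR = 0.75:

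| Control risk | RR | RD |
|---|---|---|
| 30% | 0.75/0.925 = 0.811 | −0.057 |
| 50% | 0.75/0.875 = 0.857 | −0.071 |
| 70% | 0.75/0.825 = 0.909 | −0.064 |
| 90% | 0.75/0.775 = 0.968 | −0.029 |

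The odds ratio is identical in all four rows.

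**4. Illustration.** One simulated trial of 168 infants in 18 centers of 2 to 24 infants, with true log OR −1.4 in 15 centers and +1.6 in 3. It was fitted with the SAP priors and encephalopathy term (5,000 retained draws). Under the SAP model Pr(RR<1) was 0.9878 in all 18 centers, while median RR ran from 0.63 to 0.85 and Pr(RR<0.8) from 0.34 to 0.87. The three centers with true harm, refitted with a random treatment slope (half-normal(0,1) SD):

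| Infants | Observed risk, hypothermia vs normothermia | SAP model: median RR (95% CrI) | Random slope: median RR (95% CrI) | Random slope: Pr(RR<1) |
|---|---|---|---|---|
| 20 | 70% vs 30% | 0.75 (0.55–0.97) | 1.08 (0.60–2.18) | 0.40 |
| 14 | 86% vs 71% | 0.83 (0.65–0.98) | 1.01 (0.65–1.58) | 0.48 |
| 10 | 80% vs 40% | 0.75 (0.52–0.97) | 1.14 (0.56–2.46) | 0.35 |

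Across all centers the slope model gave Pr(RR<1) from 0.35 to 0.98.

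**5. Limits of the slope model.** 168/18 = 9.3 infants per center. In five simulated trials with no heterogeneity (short runs, center risks assumed), the posterior median of the slope SD, tau, was 0.28 to 0.64, and center probabilities of benefit still spread, for example from 0.44 to 0.85. In five trials with true effects of log OR ±1.05, tau medians were 0.56 to 1.56, but two of the five showed spreads of only 0.21 to 0.57 and 0.22 to 0.72. The half-normal(0,1) prior itself has median 0.67.

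**The case against.** The strongest reply has four parts.

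First, center RR, RD and the probabilities of larger reductions do differ under the planned model. That stands. A reader might infer that no difference between sites can appear at all; the algebra does not support this. What cannot appear is a difference in the odds ratio or in direction.

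Second, the SAP never says that these plots assess consistency, and a display of how RR and RD move with center baseline risk is a coherent output of a common-odds-ratio model. That is true, but the SAP does not label the plots that way either, and a by-center forest plot without such a label will be read as a consistency check.

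Third, 6.5.8 is where the SAP puts treatment heterogeneity, center included. A reader might infer that the plan never examines heterogeneity by center; 6.5.8 shows otherwise. That analysis, however, is exploratory, conditional on estimation and unconnected to the mandatory plots, so it does not change what those plots show.

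Fourth, with so few infants per center a random slope is weakly identified and can show spread where there is none. This stands. It argues for reporting tau beside its prior and for keeping the estimation caveat in 6.5.8, since being able to fit a model with shrinkage does not make it informative. It does not make the common-effect plot informative about consistency.

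**Conclusion.** The point holds in a limited form. Followed exactly, the plan produces center plots in which, within each prior, direction and probability of benefit are equal across centers by construction, and in which the remaining variation reflects baseline risk and case mix. The equality is algebraic: it needs only the 6.5.1 model and does not rest on any simulation. The simulated figures illustrate it under assumed center sizes and deliberately strong heterogeneity, for which the SAP gives no basis; they do not estimate what this trial would show.

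A reader might go further and infer that the overall RR, RD or posterior probabilities are at fault. Nothing here supports that: the random-intercept model remains usable for the overall effect, and only the center-level display is affected. The change is worth making before analysis, but it does not alter the primary result.

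**What to change.** For the 6.5.5 center plots only, fit the same logistic model with a random treatment-by-center slope:

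`logit(p_ij) = alpha_i + theta1*enceph_ij + (theta2 + delta_i)*trt_ij`, with `delta_i ~ Normal(0, tau)`.

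State the hyperprior for tau, for example the half-normal(0,1) already used for the center SD. Report the posterior of tau beside its prior. Say with the plots that, at about 9 infants per center, tau is weakly identified and spread between centers is not in itself evidence of heterogeneity. Keep the random-intercept model for the overall RR and RD, and keep the estimation caveat in 6.5.8.

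If the slope model cannot be fitted reliably, keep the planned plots but label them as common-odds-ratio predictions that carry no information on consistency of effect across centers, and refer to 6.5.8.

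Cost: SAP wording and one extra model per prior (three fits, each giving both RR and RD); no new data. Center intervals will be wider and will come from a different model than the overall estimate, which the plot captions should state.

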In addition to adjusting for level of encephalopathy and center in the logistic model, the final analysis of the primary outcome will also perform sensitivity analyses concerning possible treatment effect confounders present at randomization. These sensitivity analyses will adjust for baseline covariates that differ across the two treatments in addition to adjusting for level of encephalopathy and center. The additional covariates will be determined by comparing the primary outcome with respect to baseline characteristics listed in Section 5.3. More details about these sensitivity analyses are given in section 6.5.7. Secondary analyses may also adjust for covariates, but in such a case the analysis will only be completed with covariate adjustment. No secondary analyses will be completed twice, in the sense of one analysis without covariates and another analysis with covariates. These analyses will use the FAS population.

The lack of preexisting data suggests that the neutral prior distribution may be most appropriate for presentation of final results; however, generation of final results of the primary outcome analysis using the skeptical (RR of 1.10) and enthusiastic priors (RR of 0.75) will also be produced for the primary outcome to give a broad overview of the implications of the trial's efficacy results. Skeptical, neutral, and enthusiastic priors will also be utilized in the analysis of primary outcome components. All non-primary or non-primary component outcomes will be analyzed using only the neutral prior.

For treatment risk difference estimation, posterior probabilities of >0%, >1%, >2%, >3%, and >5% decrease in binary outcomes will be calculated (corresponding to NNTs of 100, 50, 33, and 20). If ψ is the risk difference defined as risk in normothermia group minus risk in cooling group, then the above specified posterior probabilities are, $\Pr(\psi < 0 | X)$, $\Pr(\psi < 0.01 | X)$, $\Pr(\psi < 0.02 | X)$, $\Pr(\psi < 0.03 | X)$, and $\Pr(\psi < 0.05 | X)$. In addition to posterior probability calculations, graphical displays of the posterior distribution and appropriate 95% credible intervals for the over-all risk difference will be created. Finally, forest plots of the center level risk differences and 95% credible intervals will be created.

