In addition to adjusting for level of encephalopathy and center in the logistic model, the final analysis of the primary outcome will also perform sensitivity analyses concerning possible treatment effect confounders present at randomization. These sensitivity analyses will adjust for potential treatment effect confounders in addition to adjusting for level of encephalopathy and center. The additional covariates will be determined by comparing the primary outcome with respect to baseline characteristics listed in Section 5.3. More details about these sensitivity analyses are given in section 6.5.7. Secondary analyses may also adjust for covariates, but in such a case the analysis will only be completed with covariate adjustment. No secondary analyses will be completed twice,

in the sense of one analysis without covariates and another analysis with covariates. These analyses will use the FAS population.

The lack of preexisting data suggests that the neutral prior distribution may be most appropriate for presentation of final results of risk differences; however, generation of final results of the primary outcome analysis using the skeptical (OR of 1.10) and enthusiastic priors (OR of 0.75) will also be produced for the primary outcome to give a broad overview of the implications of the trial's efficacy results. Note, these priors are expressed on the OR scale, because the underlying model is a logistic regression model and posteriors of risk difference will be generated via post-processing. Skeptical, neutral, and enthusiastic priors will also be utilized in the analysis of primary outcome components. All non-primary or non-primary component outcomes will be analyzed using only the neutral prior.

For treatment rate ratios of count outcomes estimation, the posterior of the treatment rate ratio, ϕ , will be graphically illustrated and summarized by calculating the median treatment rate ratio, the 95% credible interval of treatment rate ratio, and $\Pr(\phi < 1 | X)$ using neutral priors. These analyses will use the FAS population.

Primary Analysis of Primary Outcome

With respect to the primary outcome, the data will be analyzed using the FAS population.

In summary the following analyses will be completed on the primary outcome:

Population	FAS					
Treatment effect	RR			RD		
Prior*	E	N	S	E	N	S

* E = Enthusiastic, N = Neutral, S = Skeptical

Each of the six analyses of the primary outcome will generate the following results:

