6.5.7 Sensitivity Analysis

In addition to adjusting for level of encephalopathy and center as a random effect, sensitivity analyses may be completed, at the discretion of the Preemie Hypothermia subcommittee, by selecting baseline covariates that differ across the two treatments. These covariates will be selected from those covariates listed in section 5.3. This analysis will only be completed for the primary outcome (death or moderate to severe disability at 18-22 months corrected age) and Death. These sensitivity analyses will be based on the FAS population.

In addition to the FAS population-based analysis, exploratory PP analyses may be done using the PP population on the primary or secondary outcomes at the discretion of the Preemie Hypothermia subcommittee, if the FAS analysis of the primary or secondary outcome results in any clinically notable findings.

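### The SAP's rules for choosing extra covariates are inconsistent and data-driven, and where a secondary outcome is further adjusted, the pre-specified model may not be run beside it

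*SAP*

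**What the plan says.** - **Planned model.** SAP 6.5.2 opens with "All regression models will adjust for" and names encephalopathy level at randomization and center as a random effect.
- **Extra covariates, 6.5.1.** A parenthesis describes added covariates as belonging to sensitivity analyses for important unbalanced baseline variables.
- **Extra covariates, 6.5.2.** "sensitivity analyses will be completed by selecting baseline covariates that differ across the two treatments".
- **Extra covariates, 6.5.5, relative-risk paragraph.** "These sensitivity analyses will adjust for baseline covariates that differ across the two treatments in addition to adjusting for level of encephalopathy and center". The next sentence reads: "The additional covariates will be determined by comparing the primary outcome with respect to baseline characteristics listed in Section 5.3". The reader is sent to 6.5.7 for details.
- **Extra covariates, 6.5.5, risk-difference paragraph.** The text is nearly the same, but the first sentence becomes "These sensitivity analyses will adjust for potential treatment effect confounders in addition to adjusting for level of encephalopathy and center". The outcome-comparison sentence follows again.
- **Extra covariates, 6.5.7.** "sensitivity analyses may be completed, at the discretion of the Preemie Hypothermia subcommittee, by selecting baseline covariates that differ across the two treatments". The section limits this to the primary outcome and Death, and does not mention comparing the outcome.
- **Secondary outcomes, 6.5.5, both paragraphs.** Covariate adjustment is optional. If it is used, only the adjusted analysis is done: "No secondary analyses will be completed twice".

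**The concern.** Imbalance between arms and association with the outcome are different selection criteria and will generally pick different variables. Two statisticians following this SAP could fit different sensitivity models and both claim to have followed it. Imbalance is also a weak criterion in a randomized trial: any observed difference is due to chance, and a variable can be imbalanced without being prognostic or prognostic without being imbalanced.

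For the primary outcome the damage is limited, because the planned result always stands beside the sensitivity result. For a secondary outcome it need not. If extra adjustment is chosen, the only model-based estimate comes from a covariate set picked from the trial's own data, and the reader cannot see what the planned model would have given.

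**Working it through.** The plan states no figure on this point, so the check is mainly a comparison of the text.

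**1. The selection rule, section by section**

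| SAP section | Criterion | Done? |
|---|---|---|
| 6.5.1 | Important and unbalanced | Not stated |
| 6.5.2 | Differs between arms | Will |
| 6.5.5, relative risk | Differs between arms, then comparison of the primary outcome | Will |
| 6.5.5, risk difference | Potential confounders, then comparison of the primary outcome | Will |
| 6.5.7 | Differs between arms | May, at subcommittee discretion |

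No section defines a measure of difference, a cut-off or a way to combine the criteria. Section 6.5.7, which is meant to hold the details, omits the outcome comparison. The pool in 5.3 is described only as an example list.

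**2. Secondary outcomes**

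- 6.5.2 requires the encephalopathy-plus-center adjustment in every model.
- 6.5.5 says that a secondary analysis given extra covariates is run only in that form. The planned model on its own is then not run.
- 6.5.7 restricts extra adjustment to the primary outcome and Death and calls it a sensitivity analysis. On that text, no other secondary outcome would be further adjusted.
- Death is listed among the secondary outcomes in 6.4. A base analysis plus a sensitivity analysis of Death makes two analyses of a secondary outcome, which 6.5.5 rules out.
- Elsewhere 6.5.5 says that secondary outcomes follow the same process as the primary outcome, which would include the base model.

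These statements cannot all be followed.

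**3. Missing covariate values**

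Section 6.6 allows no imputation, the note to 5.3 expects missing baseline data, and 5.1 admits infants with no blood gas result. Unless another method is stated, adding a blood gas covariate drops those infants. An adjusted-only secondary result could then rest on fewer infants, with no full-set result beside it.

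**4. Illustration of how far the rules can diverge**

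From the SAP: 168 infants, the neutral prior Normal(0, 0.7072) on the log odds ratio, Normal(0, 1) priors on the other terms, and the 0.80 posterior-probability level used in 3.4. Assumed, and not in the SAP: 84 infants per arm, 30% severe encephalopathy, independent normal covariates, selection at |z| > 1.96, a normal approximation to the posterior, and no center effect. Each scenario has 3,000 simulated trials with no treatment effect. Entries are the proportion with Pr(benefit) ≥ 0.80.

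| Candidates (prognostic, coefficient) | Planned model | Imbalance rule | Outcome rule | Two rules disagree about 0.80 | Median absolute difference in Pr(benefit) between rules |
|---|---|---|---|---|---|
| 50 (10, 0.3) | 0.163 | 0.158 | 0.150 | 0.079 | 0.073 |
| 30 (5, 0.4) | 0.143 | 0.145 | 0.144 | 0.071 | 0.064 |
| 50 (0) | 0.153 | 0.147 | 0.149 | 0.060 | 0.053 |

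The rules chose different covariate sets in at least 99% of trials. Either rule, applied without choice, leaves the null rate about where the planned model has it. If the more favourable of the planned and imbalance-selected models could be reported, the rates would be 0.190, 0.162 and 0.174, which is 0.027, 0.019 and 0.021 above the planned model. So the cost comes from the freedom to choose, not from either rule alone.

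**The case against.** **The primary result is safe.** A reader might infer that the main efficacy estimate can be shaped by covariate selection. The documents do not support that. The six FAS analyses of the primary outcome use the fixed model, and extra covariates enter only as additional sensitivity analyses. This stands.

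**The two criteria may be one.** Section 6.5.5 introduces these analyses as concerning confounders, and a confounder is related to both treatment and outcome. The two sentences could be joint conditions. That reading is possible, so it goes too far to call the rules necessarily opposed. But the SAP never says that both must hold, and 6.5.2 and 6.5.7 give imbalance alone.

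**Selection need not use treatment assignment throughout.** A reader might infer that every version requires data by arm. The imbalance rule does. The outcome comparison can be done pooled over arms, and the trial being open-label does not show how selection will be carried out.

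**Loss of the planned model is conditional.** It follows only if adjustment is chosen, and under 6.5.7 it would not arise for most secondary outcomes. Section 6.5.1 also has outcomes summarized descriptively, so crude frequencies remain. It would be wrong to say that the planned model will never be reported.

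**The ban on two analyses may be a safeguard.** Followed literally, it prevents fitting both models and keeping the better one, so the best-of-two figures above are not what compliance would produce. But it leaves the choice of whether to adjust, and for what, to be made once data are in hand, and it removes the comparison by which a reader could judge that choice.

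**Death may count as a component.** Sections 6.5.3 and 6.5.5 treat components of the primary outcome separately for priors, so Death might be thought exempt. No exemption is stated, and 6.4 lists Death as secondary.

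**Conclusion.** The concern holds in limited form. The covariate rule is stated inconsistently, selects from the trial's own data without a threshold, and is mandatory in two sections but discretionary in a third. For the primary outcome this affects sensitivity analyses only. For secondary outcomes, 6.5.5 as written lets a data-selected model replace the pre-specified one, and it conflicts with 6.5.7 on whether extra adjustment is allowed there at all.

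The documents do not allow the effect to be sized. The simulated differences rest on an assumed cut-off, independent covariates and assumed prognostic strengths. For the same reason, no count of covariates expected to differ by chance can be attributed to this SAP, which states no screening level. The conclusion rests on the text and does not need those figures. This should be corrected, but it does not put the main result in doubt.

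**What to change.** 1. In 6.5.1, 6.5.2, 6.5.5 and 6.5.7, replace the screening rules with one short list of prognostic covariates from Section 5.3, chosen by the subcommittee without reference to data by arm. Gestational age, sex, inborn or outborn status and first blood gas are examples only. State how infants with missing covariate values are handled.
2. Report the encephalopathy-plus-center model for every secondary outcome. Any further-adjusted result is additional and labelled as a sensitivity analysis.
3. In both 6.5.5 paragraphs, delete the sentence confining an adjusted secondary analysis to its adjusted form, and the sentence beginning "No secondary analyses will be completed twice".
4. Reconcile 6.5.5 with 6.5.7 on which outcomes receive extra adjustment, and 6.5.2 and 6.5.5 with 6.5.7 on whether it will or may be done.

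The cost is SAP wording, a few extra model runs and slightly longer tables. No new data are needed.
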